9.5.2 Sample size

In the initial plan, it was planned to recruit 1200 patients in total for the 3 waves in the selected European countries, depending on the reimbursement status of Praluent in each country, ie, about 400 patients per wave.

According to the feasibility results, the number of physicians might be limited in each country. The initial estimate was that a minimum of 100 physicians were needed to reach the recruitment goal of 400 patients per wave. It was anticipated that given the uncertainty of Praluent market penetration in each country, the number of sites might need to be adjusted in order to reach the target of 400 patients per wave.

b 42.7% is the percentage of patients with at least one very low LDL-C (<25 mg/dL or <0.65 mmol/L) observed in the Phase 2 and 3 trials.

In 2018, the MAH encountered challenges in Wave 1 recruitment that prevented it from reaching the target sample size in the anticipated timeframe. Despite the remediation actions taken by the MAH, the site enrollment projections demonstrated that the initial plan of recruiting 400 patients from 100-138 sites for Wave 1 could not be accomplished due to continued lower than expected positive site response rate, low Praluent prescriptions, and limited patient eligibility period of 4 months from March 2017 to June 2017 for the first Praluent prescription. Therefore, the MAH decreased the projected number of sites and patients enrolled in Wave 1 to 25 sites and 75 patients, as base case (or at the minimum), and 30 sites and 90 patients, as best case, assuming an average of 3 patients per site. Reducing the number of patients in Wave 1 to 75 impacted the precision of the proportion estimate; the half-width of the 95% confidence interval was enlarged from a maximum half-width of 4.9% to 11.8%, which was still deemed sufficient at that stage in the study. For Wave 2 and Wave 3, minimum 90 sites and 400 patients were deemed feasible for enrollment at that time.

Twenty sites enrolled 68 patients in Wave 1 and 61 sites enrolled 251 patients in Wave 2. Although the remediation actions as outlined in Amended protocol 01 (December 21, 2018) (Annex 3) are being taken during Wave 3 enrollment, the target total sample size of 875-890 will not be reached at the end of the recruitment period of the Wave 3. Based on the current projection, the total number of sites enrolled in Wave 3 is expected to be ranging from 36 to 63 due to both recruitment challenges and the impact of Coronavirus disease 2019 (COVID-19) at the time of sites selection, and these sites are expected to enroll 135 to 255 patients. Best efforts will be made to enroll as many eligible patients as possible, not limiting to 255 in Wave 3. The total number of patients enrolled in this study is expected to range from approximately 454 to 574 (Table 1).

9.6 DATA MANAGEMENT

9.6.1 Data collection schedule

Data will be retrospectively collected after the end of each of the 3 observation periods and after the physicians have been selected and recruited for participation.

9.6.2 Data collected

Please refer to Section 9.3.

9.6.3 Site/Physicians questionnaire

Physicians who will not accept to participate will be described (specialty and level of prescriptions, reason for refusal, where available).

For physicians who will accept to participate, a physician questionnaire will be put in place to collect the physician's data mentioned in Section 9.3.1, and the potential availability of critical variables, such as LDL-C values, that need to be collected. An ad hoc question will be included in the Site Information Questionnaire used at Site Selection in order to qualify sites for participation.

9.6.4 Patient/Subject tracking log

A tracking log will be used to specify the reason for non-inclusion of the non-enrolled patients. To comply with data privacy requirement, data collected on the tracking log will be fully anonymous:

- Patient number (#): 1, 2....
- Included: Yes/No.
- Reason for non-inclusion.

9.6.5 Patient data

Data collected are mentioned in Section 9.3.

9.7 DATA ANALYSIS

This section provides specifications for preparation of final Statistical Analysis Plan (SAP), which will be issued prior to database lock of the first wave. Any differences compared to this statistical section should be identified and documented in final SAP.

9.7.1 Primary analysis

Descriptive analyses will be conducted for each wave separately. In addition, analyses will be conducted using the entire data of all 3 waves.

Point estimates of proportions and 95% confidence intervals will be calculated.

Data will be summarized using mean, first quartile, median, third quartile, standard deviation and range for continuous parameters and counts, percentages and 95% confidence intervals if needed for categorical parameters. The analyses will be performed, overall, by countries, and for specific analyses (starting dose of Praluent, occurrence of very low LDL-C level) will also be presented based on baseline LDL-C levels.

The following descriptive analyses will be presented on the eligible population:

A. Occurrence of very low LDL-C level

An LDL-C level <25 mg/dL (0.65 mmol/L) is defined as very low; and an alternative definition with a cut-off at 15 mg/dL (0.39 mmol/L) will also be used.

For each definition of very low LDL-C level, the following statistics will be calculated:

- 1. The proportion of patients who have at least 1 very low LDL-C level during the 6-month observational period:
 - (1) In the whole analysis population,
 - (2) According to baseline LDL-C level (<70; 70 to <100; 100 to <130; 130 to <160; 160 to <190; ≥190 mg/dL),
 - (3) According to Praluent starting dose.
- 2. All occurrences of very low LDL-C levels will be classified according to the Praluent regimen received at the time of the corresponding LDL-C test.

B. Evolution of LDL-C level after the occurrence of very low LDL-C level

- 1. Among the patients who have a LDL-C level of <25 mg/dL (0.65 mmol/L) at any dose, the proportions of patients whose LDL-C level returns to ≥25 mg/dL (0.65 mmol/L) within 8 weeks after the lab test, if data available, and at any time until the end of the 6-month observational period after index date, respectively.
 - (1) Overall,
 - (2) By the action of dosage regimen modification or discontinuation of Praluent, or change in dosing frequency of Praluent, or lowering doses of other lipid-lowering drugs, or discontinuation of other lipid-lowering drugs.
- 2. Same analysis will be conducted for the patients who have LDL-C level <15 mg/dL (0.39 mmol/L).

C. Change in treatment after the occurrence of very low LDL-C level

For each definition of very low LDL-C level, the following statistics will be calculated:

Among the patients who have a very low LDL-C level at a specific dosage regimen, within 8 weeks after the lab test and at any time until the end of the 6-month observational period after index date, respectively:

- (1) The proportion of patients for whom the dose of Praluent is changed to another dose regimen,
- (2) The proportion of patients for whom Praluent is discontinued,
- (3) The proportion of patients for whom the dosing frequency of Praluent is changed at least once,
- (4) The proportion of patients for whom the doses of other lipid-lowering drugs are decreased at least once,
- (5) The proportion of patients for whom other lipid-lowering drugs are discontinued,
- (6) The proportion of patients for whom no change in Praluent treatment or dose and/or other lipid-lowering drugs have been made.

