9.2.2 Eligibility criteria

9.2.2.1 Inclusion criteria

Physicians who meet the following inclusion criterion will be eligible to participate in this study:

I 01. At least one initial prescription of Praluent during the eligibility period.

Eligible patients for retrospective data collection will be those meeting the following criteria:

- I 02. Initiated with Praluent following a first prescription during the eligibility period.
- I 03. Signed written informed consent, if it is required by the country.

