9.2.2.2 Exclusion criteria

Physicians who meet one or more of the following exclusion criteria will be excluded from this study:

- E 01. Have participated in any randomized clinical trials with Praluent (alirocumab).
- E 02. Have participated in a previous wave of this study.

Patients who meet one or more of the following exclusion criteria will be excluded from this study:

- E 03. Have participated in any randomized clinical trials with Praluent (alirocumab).
- E 04. Medical chart not retrievable, empty or missing.

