9.2.3 Analysis populations

The analysis population will consist of all patients included in the study and meeting all inclusion criteria. This population will be the eligible population.

Physicians who included at least one patient in the patient analysis population will be part of the physicians' analysis population.

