9.5 STUDY SIZE

9.5.1 Determination of sample size

According to the global pool of Phase 2 and Phase 3 studies, 42.7% of patients treated with Praluent (alirocumab) had at least 1 value of LDL-C <25 mg/dL¹, regardless of the dose of Praluent received and the baseline LDL-C level. Compared to what is expected in the real clinical practice, this percentage is probably overestimated as the very low LDL-C levels occurred mostly during the Long Term study in which patients were initiated and maintained at 150 mg throughout the study, independent of the LDL-C baseline, to evaluate the long term safety of Praluent administered at the highest dose. In Wave 1 of the study, a total of 61 patients had at least one LDL-C value available during the 6-month observation period (irrespective of baseline LDL-C data availability); among those, three patients (4.9%) had an LDL-C level of <25mg/dL.

The following table shows the exact 95% confidence intervals for a range of possible proportions of patients with very low LDL-C value for different study sizes (<25 mg/dL or <0.65 mmol/L). For the global analysis gathering the 3 waves with total number of patients ranging from approximately 454-574 and assuming approximately 5% of the patients will have an LDL-C level of <25 mg/dl based on the observed data for Wave 1, the half-width will range from 1.85% (95% CI = 3.4, 7.1) to 2.1% (95%CI=3.2, 7.4) for the observed proportion of 5% (Table 3), which is deemed sufficient.

¹ In the clinical trials, only patients who achieve 2 consecutive calculated LDL-C <25 mg/dL were monitored according to a specific process and only these figures were presented in each CSR and submitted files.

09-Jul-2020 Version number: 1

Table 3 - Exact 95% confidence intervals for different study sizes and possible proportions of patients with very low LDL-C level (%)

% patients with very low LDL-C	Number of Patients						
	68	135	251	255	454	574	875 (total number planned in 2018)
1	0 , 7.1	0.1 , 4.5	0.2 , 3.2	0.2 , 3.1	0.3 , 2.4	0.4 , 2.2	0.5, 1.9
2	0.1,8.8	0.4,6	0.7 , 4.6	0.7 , 4.6	0.9, 3.8	1,3.5	1.2, 3.2
5 ^a	1.2 , 13.2	2,10.2	2.7 , 8.5	2.7 , 8.4	3.2 , 7.4	3.4 , 7.1	3.7, 6.7
10	4 , 19.7	5.5 , 16.3	6.6 , 14.4	6.6 , 14.4	7.4 , 13.1	7.7 , 12.8	8.1, 12.2
20	11.3 , 31.5	13.6 , 27.7	15.2 , 25.5	15.3 , 25.4	16.4 , 24	16.8 , 23.5	17.4, 22.8
30	19.5 , 42.3	22.4 , 38.5	24.4 , 36.1	24.4 , 36	25.8 , 34.4	26.3 , 33.9	27.0, 33.2

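### The primary proportion has two incompatible denominators: all eligible patients in Section 9.7.1, LDL-C-tested patients in Section 9.5.1

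*Protocol*

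**What the plan says.** Section 9.7.1 presents its analyses on the eligible population. Item A.1 is "The proportion of patients who have at least 1 very low LDL-C level during the 6-month observational period", given first "In the whole analysis population" and then by baseline LDL-C and by starting dose. Section 9.2.3 defines that population: "The analysis population will consist of all patients included in the study and meeting all inclusion criteria".

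Neither the inclusion nor the exclusion criteria ask for an LDL-C result. Apart from consent where a country requires it, a patient qualifies by being "Initiated with Praluent following a first prescription during the eligibility period" (Section 9.2.2.1). The only data-related exclusion in Section 9.2.2.2 is "Medical chart not retrievable, empty or missing".

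Section 9.5.1 counts differently. For Wave 1, "a total of 61 patients had at least one LDL-C value available during the 6-month observation period", and three of those 61 were below 25 mg/dL, reported as 4.9%. Footnote a of Table 3 repeats this. Section 9.5.2 gives the enrolled number: "Twenty sites enrolled 68 patients in Wave 1". Section 9.5.1 then takes about 5% from Wave 1 as its planning rate and states precision "For the global analysis gathering the 3 waves with total number of patients ranging from approximately 454-574". Those totals count enrolled patients, as do the 68 and 251 that head columns of Table 3.

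**The concern.** The study judges whether the dosing recommendations avoid very low LDL-C, so its headline number is how often very low values occur. A patient with no LDL-C test in the six months cannot show a very low value. If that patient still counts in the denominator, the proportion can only fall, and the recommendations look more effective than the data show.

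The same mechanism affects comparisons. Section 9.7.1 reports by country, baseline LDL-C and starting dose, and Section 9.2.1 wants trends across the three waves. If the share tested differs between these groups, a difference in testing could look like a difference in risk.

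If tested patients are the intended denominator, the estimate is not diluted. But Section 9.5.1 then pairs a rate among the tested with a count of the enrolled, and the stated precision rests partly on patients who cannot supply an outcome.

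**Working it through.** **Inputs.** Wave 1: 68 enrolled (9.5.2), 61 tested and 3 below 25 mg/dL (9.5.1). Planning rate 5%, projected totals 454 and 574, exact two-sided 95% intervals (9.5.1, Table 3). The tested share for Waves 2 and 3 is not given.

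**1. The protocol's own precision.** Clopper-Pearson limits are the 2.5% quantile of Beta(x, n − x + 1) and the 97.5% quantile of Beta(x + 1, n − x). The published limits are matched with x = 0.05n left unrounded.

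| n | Recomputed 95% CI | Half-width | Stated |
|---|---|---|---|
| 454 | 3.19 to 7.43 | 2.12 | 3.2 to 7.4; 2.1 |
| 574 | 3.37 to 7.11 | 1.87 | 3.4 to 7.1; 1.85 |

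The stated 1.85 is half the difference of the rounded limits. The arithmetic is right for the n used.

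**2. The two denominators in Wave 1.**
- Tested: 3/61 = 4.92% (exact CI 1.0 to 13.7).
- All enrolled: 3/68 = 4.41% (exact CI 0.9 to 12.4).
- Untested: 68 − 61 = 7, and 7/68 = 10.3%. The relative understatement is 1 − 61/68 = 10.3%.
- Extremes over the 68: from 3/68 = 4.4% if none of the 7 was very low to (3 + 7)/68 = 14.7% if all were.

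**3. Dilution if 9.7.1 is followed literally.** Reported proportion = rate among tested × share tested. For 5% among the tested:
- share 90%: 4.5%
- share 80%: 4.0%
- share 60%: 3.0%

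Two groups with the same 5% among the tested, but assumed tested shares of 70% and 95%, would be reported as 3.5% and 4.75%. The shares in this step are illustrations; the documents give none by group.

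**4. Precision if tested patients are meant.** Carrying 61/68 = 89.7% forward: 454 × 61/68 ≈ 407 and 574 × 61/68 ≈ 515.

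| Enrolled | Tested | 95% CI at 5% | Half-width | On enrolled n |
|---|---|---|---|---|
| 454 | 407 | 3.10 to 7.59 | 2.25 | 2.12 |
| 574 | 515 | 3.28 to 7.25 | 1.98 | 1.87 |

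Over assumed tested shares from 95% down to 60%, the half-width runs from 2.18 to 2.79 (454 enrolled) and from 1.93 to 2.46 (574 enrolled).

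**The case against.** The strongest defence is that the phrase for the overall line in A.1 only separates it from the breakdowns beneath it, and that the protocol's one worked result on this endpoint leaves untested patients out. Section 9.7 also describes itself as a specification for a SAP, which is not shown here and may settle the matter. Availability of LDL-C values is checked at site selection (9.2.4.1, 9.6.3), and patterns of missing data are to be checked regularly (9.9).

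Part of this stands. A reader might infer that the protocol classifies untested patients as not very low. It nowhere says so; that follows only from applying its stated population literally. The Wave 1 figure is real evidence that tested patients may be intended.

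It does not remove the contradiction. Where the protocol wants to restrict to patients with data, it says so: 9.7.1 B.1 makes the eight-week return conditional on available data, and 9.7.2 C takes the mean time to test in patients who had one. Item A.1 carries no such condition. This is therefore not silence left for the SAP; two sections of one document disagree. The site-level checks did not prevent 7 of 68 Wave 1 patients from having no value.

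**Conclusion.** The inconsistency is established, and the denominator of the primary proportion should be fixed in the protocol text. The case rests on that denominator rather than on the half-width.

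It would be tempting to conclude that the estimate is biased downward and that the precision uses the wrong n as well. The documents do not support both at once. With all eligible patients as the denominator, the proportion is diluted, but 454 to 574 is then the proper n for it. With tested patients, n is too large, but there is no dilution.

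Under the literal reading, Wave 1 is 4.4% instead of 4.9%, modest against an exact interval of 1.0 to 13.7. Under the other reading, half-widths widen by a little over 0.1 point, which does not by itself overturn the protocol's judgement that precision is adequate.

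The figures of 407 and 515 assume that the Wave 1 tested share holds in waves with different countries and a 12-month eligibility window. They also take the projected totals as given, although Wave 2 may gain 25 patients and Wave 3 is not capped at 255. How far testing differs between countries or starting doses is not documented, so distorted comparisons are a possibility and not a finding. Severity: should be fixed.

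**What to change.** - **Section 9.7.1 A:** define the primary denominator, overall and in every stratum, as eligible patients with at least one LDL-C value after the index date and within the observation period.
- **Reporting:** give the number and percentage untested by wave, country and starting dose.
- **All-eligible proportion:** keep it as a secondary figure, labelled a lower bound.
- **Limitation:** state that restricting to tested patients does not remove selection in who is tested.
- **Section 9.5.1 and Table 3:** state precision on the expected number tested, with the assumed share shown. If 61/68 holds, that is about 407 to 515 patients and half-widths of about 2.25 to 2.0 points.

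The cost is wording in two sections and one table, plus a short count of untested patients in the reports. No new data are needed. The stated precision becomes slightly less favourable.

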9.2.1 Duration of the study

The study will be conducted in 3 waves during 3 consecutive years.

The rationale for conducting the 3 waves when treatment patterns are evaluated across 3 different cohorts of Praluent prescribers and their patients is as follows:

- To confirm the effectiveness of the SmPC dosing recommendations risk minimization measures observed in the repeated waves.
- To observe the trend in practice over time, if any, by comparing findings across the 3 waves.
- Using 3 waves will also allow getting preliminary data available sooner, with the earliest availability at the end of the first wave.

After the first Praluent prescription identified during the eligibility period (Mar to Jun 2017 for Wave 1, Jul 2017 to Jun 2018 for Wave 2, and Jul 2018 to Jun 2019 for Wave 3), the observation period will last 6 months for each patient: from their first prescription to 6 months later, at the latest until the end of December 2017, 2018 and 2019, respectively.

After the end of the 6-month observation period, submission of appropriate documentation to Regulatory Authorities (if applicable according to local regulations) and/or Ethics Committees will be performed, in parallel, the physicians will be enrolled and informed of the main purpose of the study and upon all relevant approvals are obtained, the patients will be selected up to the first quarter (Q1) of 2019, 2020, and 2021 following the observation period, respectively.

The data will be collected retrospectively from the second quarter (Q2) 2018 to Q1 2019 in Wave 1, from Q1 2019 to Q1 2020 in Wave 2 and from Q1 2020 to Q1 2021 in Wave 3, respectively. Please see details in Figure 1 and Figure 2.

Figure 1 - Annual study progress in Wave 1

Wave 1

[figure not shown]
[figure not shown]

Figure 2 - Annual study progress in Waves 2 and 3

Waves 2 and 3

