9.3.7 Adverse events

An adverse event (AE) is any untoward medical occurrence in a patient or in a clinical investigation subject administered a pharmaceutical product, and which does not necessarily have a causal relationship with that treatment. An adverse event can thus be any abnormal laboratory finding, symptom or disease temporally associated with the use of a medicinal (investigational) product, whether or not caused by that product.

Adverse events will be collected from the initiation of Praluent until the end of the 6-month observational period with the following details:

- 1. Nature of AE, such as hospitalization, onset of new disease, a new symptom, worsening of an existing condition, or lab abnormalities...
- 2. Start date/end date and outcome
- 3. Action taken with Praluent, if any: discontinuation, delay, or dose change.

9.3.8 Date on which the patient is no longer managed by the treating physician

Date on which the patient is no longer managed by the treating physician will be collected, if it is applicable.

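### Section 9.7.1 C keeps patients with less than 8 weeks of observation left in its 8-week denominators, which biases 'no change' upward; B.1(2) does not order action and recovery in time

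*Protocol*

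**What the plan says.** All references are to the protocol; the SAP is not shown.

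Section 9.2.1 fixes follow-up: "the observation period will last 6 months for each patient: from their first prescription to 6 months later". Section 9.3 limits collection of patient variables to that period.

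Section 9.7.1 C sets both the denominator and the first window: "Among the patients who have a very low LDL-C level at a specific dosage regimen, within 8 weeks after the lab test". The same outcomes are then reported to the end of the 6 months; the timing in full is "within 8 weeks after the lab test and at any time until the end of the 6-month observational period after index date, respectively". Item (6) is "The proportion of patients for whom no change in Praluent treatment or dose and/or other lipid-lowering drugs have been made". C sets no minimum remaining observation, no censoring and no condition on data availability.

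Section 9.7.1 B does set a condition for the return of LDL-C to the threshold: "within 8 weeks after the lab test, if data available, and at any time until the end of the 6-month observational period". Item B.1(2) then splits recovery "By the action of dosage regimen modification or discontinuation of Praluent, or change in dosing frequency of Praluent", or by reduction or discontinuation of other lipid-lowering drugs. The order of the action and the recovery test is not stated.

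Section 9.3.8 adds a possible earlier end of observation: "Date on which the patient is no longer managed by the treating physician will be collected, if it is applicable". Neither B nor C uses that date. Section 9.7.2 plans Kaplan-Meier estimates for regimen modification and for LDL-C test timing.

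**The concern.** C reports a proportion over a fixed 8-week window, but some patients cannot be watched for 8 weeks. A change made after the cut-off is never recorded, so followed as written the patient falls under (6). The error has one direction. For these patients the 8-week window and the window to the end of observation are also the same, so the two reported proportions stop measuring different things.

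In B.1(2), an action taken after LDL-C has already recovered can be tabulated with that recovery. Patients with longer remaining follow-up also have more opportunity for both an action and a recovery. Together these can make an action look associated with recovery when it had no effect.

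B and C are listed as primary analyses, and they follow patients forward from a very low value. Few patients will enter them, so a handful of misclassified patients moves the percentages visibly.

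**Working it through.** **Inputs from the protocol.** Follow-up of 6 months, taken as 365.25/2/7 = 26.09 weeks (Section 9.2.1). Window of 8 weeks (Section 9.7.1). Total of 454 to 574 patients with about 5% having LDL-C <25 mg/dL (Section 9.5.1).

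**The plan's own figures.** The protocol gives no figure for the 8-week outcomes. Its precision statement for the 5% rate reproduces with exact (Clopper-Pearson) limits: 3.19% to 7.43% at N = 454 and 3.37% to 7.11% at N = 574, against the stated 3.2 to 7.4 and 3.4 to 7.1. The Wave 1 rate is 3/61 = 4.9%.

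**Patients in B and C.** 0.05 × 454 = 22.7 and 0.05 × 574 = 28.7, so about 23 to 29 if every patient has an LDL-C value after the index date.

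**Latest test with a full window.** 26.09 − 8 = 18.09, so about week 18.

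**Share truncated (assumption: first very low tests spread evenly from week a to week 26.09).** s = 8/(26.09 − a):
- a = 0: 8/26.09 = 31%
- a = 4: 8/22.09 = 36%
- a = 8: 8/18.09 = 44%

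In patients, this runs from 23 × 0.307 = 7.1 to 29 × 0.442 = 12.8, or about 7 to 13.

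**Effect on 'no change' (further assumption: constant hazard of change).** Let p be the true 8-week change rate and H = −ln(1 − p). Averaged over remaining windows of 0 to 8 weeks, a truncated patient shows a change with probability 1 − p/H. Observed change is therefore (1 − s)p + s(1 − p/H). Example with p = 0.40 and a = 4: H = 0.511, 1 − 0.40/0.511 = 0.217, and 0.638 × 0.40 + 0.362 × 0.217 = 0.334. 'No change' reads 66.6% instead of 60%.

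| True change | True 'no change' | Reported, a = 0 | a = 4 | a = 8 |
|---|---|---|---|---|
| 20% | 80% | 83.0% | 83.5% | 84.3% |
| 40% | 60% | 65.6% | 66.6% | 68.1% |
| 60% | 40% | 47.8% | 49.2% | 51.3% |
| 80% | 20% | 29.1% | 30.8% | 33.1% |

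The overstatement runs from 3.0 to 13.1 points.

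**A less even spread.** With 70% of tests in weeks 4 to 12 and 30% in weeks 12 to 26 (week 26 as the end), the truncated share is 0.30 × 8/14 = 17%. A true 50% change rate, evenly timed within the 8 weeks, then reads 0.50 × (0.829 + 0.171 × 0.5) = 46%. If all tests fall at weeks 4 to 8, no window is cut by the 6-month limit.

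**By-action split with no true effect.** Simulation with tests uniform over weeks 4 to 26.09 and independent exponential times to action and to recovery. The (action, recovery) 8-week rates were (40%, 50%), (20%, 50%) and (40%, 30%). To the end of follow-up, recovery was 67%, 68% and 45% in patients with an action, against 46%, 51% and 29% without. In the action group, 53%, 57% and 47% of recoveries came before the action. The whole difference is artefact.

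**The case against.** The strongest reply is that evaluable denominators, censoring and date ordering are SAP matters. That would settle a gap, but C is not silent: it states a denominator and a window. Section 9.7 says its text specifies the SAP and that differences must be documented. For B.1(2) the reply has more weight. An action can naturally be read as the response to the very low value, and no rule says that later actions count. The point there is an ambiguity to close.

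Four stronger readings are tempting and are not supported.

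- A reader might infer that the 8-week recovery outcome in B is biased in the same way. Its data-availability condition allows patients without a follow-up value to be left out, so it is partly protected. The condition is vague, however, and does not require a full 8 weeks.
- A reader might equate 'no change' with the dosing recommendation not being followed. The label text quoted in Section 7.1 is permissive and names no action for LDL-C <25 mg/dL.
- A reader might take B and C as the only evidence on prescriber reaction. Section 9.7.2 also reports very low LDL-C before discontinuation, reasons for discontinuation, and LDL-C before and after regimen modification.
- A reader might take a figure near 36% truncated as expected. It rests on an even spread that the protocol does not give. The only timing quoted, 4 to 8 weeks after initiation or titration, points to less truncation, although that wording is also permissive and covers later titrations.

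It is also fair that the analyses are descriptive. With 23 to 29 patients the exact 95% interval around 50% is about ±19 to 21 points, wider than the bias. Bias is not reduced by that, and here it is avoidable.

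**Conclusion.** The concern holds for the 8-week outcomes in C. As written, patients tested after about week 18 stay in the denominator with a shortened window, so (1) to (5) are biased down and (6) up. The direction follows from the text. The size does not: it is about 3 to 13 points under evenly spread tests and true change rates of 20% to 80%, and small if most tests fall at weeks 4 to 8. It also holds that B.1(2) leaves the order of action and recovery open. The occurrence analysis in A is unaffected, and no sample size changes. This is a correction worth making to a primary descriptive analysis. It does not undermine the study.

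**What to change.** **C, 8-week outcomes.** As the main figure, do one of the following:
- Include only patients with at least 8 weeks between the first very low test and the earlier of the 6-month date and the Section 9.3.8 date.
- Keep all patients and estimate at 8 weeks with censoring at that earlier date. Use Kaplan-Meier for any change against no change (6). Use cumulative incidence with Praluent discontinuation as a competing event for (1) and (3), because discontinuation precludes a later regimen or frequency change and plain Kaplan-Meier would overstate them.

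Show the number excluded or censored.

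**B, 8-week recovery.** State that the availability condition means an LDL-C test within the 8 weeks after the very low value.

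**B.1(2).** Count an action only if it is dated after the very low test and before the test that first shows return to the threshold or above, or before the last LDL-C test if there is no return. Cutting off at the next test would be wrong: a patient with a second very low value, then an action, then recovery would be listed under no action. Even when ordered, the split stays descriptive, since patients who recover early have had less time to receive an action.

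**Cost.** Only wording in Section 9.7.1 changes; test, prescription, renewal and discontinuation dates are already collected. Under the even-spread assumption, the restriction leaves about 13 (23 × 0.558) to 20 (29 × 0.693) patients and wider intervals. The censored version keeps all of them.
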